Adverse pregnancy outcome: A secondary analysis from the Partners PrEP study found no differences between women with incident pregnancies while taking PrEP in rates of preterm birth, congenital anomalies, or infant growth in the first year of life and women taking placebo; however, all women stopped the study medication at time of pregnancy detection, which occurred a median of 35 days (IQR: 29–45) after conception [36]. The rates of adverse birth outcomes did not differ according to study arm (78). The Partners Demonstration Project, an open-label delivery study in Kenya and Uganda, HIV-uninfected women in serodiscordant relationships were given the option of continuing PrEP even after pregnancy was diagnosed. Of the 34 who became pregnant, 30 elected to continue PrEP antenatally. When compared to 96 women who became pregnant in the Partners PrEP clinical trial, there were no differences in pregnancy loss, preterm delivery, or congenital anomalies, though sample sizes were small [36].

HIV and pregnancy in young women: Young South African women aged 15–24 years contribute nearly 30% of all new HIV infections in the region. In South Africa, this percentage translates to 113,000 new infections in young women per year, more than four-times the number contributed by their male peers (Figure 2). Further, adolescent girls have high pregnancy rates in South Africa. Approximately 3.7% of 16-year-old girls and 7% of 17-year-old girls were pregnant in 2013 (Figure 3).

Our study proposes to enroll pregnant adolescents 16-19 who have a parent or guardian who provides consent to their participation in the study. The specific age range – enrollment of adolescent and young women 16-19 years – covers a critical period of risk of HIV acquisition. This age range falls squarely within the period of adolescence defined by the World Health Organization as 10-19 years of age. Because of the high HIV incidence and existing policy supporting PrEP among adolescent girls, it would be unethical

to not provide adolescent girls and young women with PrEP that might prevent them from acquiring HIV [18].

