Setting. The study will take place in two urban townships in Cape Town (Gugulethu MOU) with high HIV incidence that span the different socioeconomic, cultural, and ethnic groups in South Africa. We selected this community because of the high HIV prevalence there in pregnant and breastfeeding women, and because of the high number of mothers visiting every month for ANC and labour/delivery. Further, our team has several years' experience implementing research studies in those MOUs which will facilitate the integration of the study there. In 2017, Gugulethu saw over 3300 new ANC consultations per month, and 72% (n=2300) are HIV-negative. Considering our experience and patient flow, we are confident that at least 60 women/month per facility can be enrolled. Further, Drs. [name], [name] and colleagues have conducted research in the Gugulethu community for more than a decade and have substantial experience partnering with local health services. Building on this platform, we will use existing infrastructure in each clinic, including capacitating existing clinical providers, pharmacists and counselors, to provide PrEP care to pregnant and breastfeeding mothers. We will hire study staff to assist in the coordination, data management, and overall quality assurance of the counseling, drug provision and participation follow-up.

4. Study population

Study counselors will enroll consecutive eligible, consenting pregnant adolescent girls (≥ 16 years) and women in ANC (N=220 pregnant women) and follow them up for 12-months postpartum or until censorship for a mean of 18-months' follow-up.

Inclusion Criteria:

1. ≥ 16 years old
2. confirmed HIV-negative (using 2 rapid HIV test kits, confirmed with a 4th generation antigen HIV test),
3. lives within 20 kilometers of a clinic

4. confirmed to be pregnant
5. without psychiatric or medical contraindications to PrEP

Exclusion criteria:

Individuals not meeting the above criteria or meeting any of the following criteria will be excluded:

- Concurrent enrolment in another HIV-1 vaccine or prevention trial
- Medical hospitalization in the past year for any reason
- Receipt of TB treatment within the past 30 days
- History of renal disease
- Exhibiting psychotic symptoms (including hallucinations, suicidal or homicidal ideations, or violent behaviour)
- Currently or history of taking an anti-psychotic medication (such as for treatment of bipolar disorder, schizophrenia, or postpartum psychosis following a previous pregnancy)

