- Positive Hepatitis B surface antigen (HBsAg) test on screening
- History of bone fracture not related to trauma
- Any other medical, psychiatric or social condition which in the opinion of the investigators would affect the ability to consent and/or participate in the study.

Study censorship will include:

1. Seroconversion
2. Moves away
3. Transfers out of care
4. Lost to follow up (e.g. does not return for study or clinical visit for >8 weeks and study staff are unable to track the participant, or she does not want to continue in the study).

Eligible, consenting women will receive R100 in grocery vouchers per visit for their time and effort in the study as well as additional money to cover the cost of transport to each study visit. All participants will also receive minor refreshments (e.g. sandwich and cool drink) on the day of their visit.

Procedures for the informed consent process are outlined below. Throughout, trained study staff will ensure that women are aware of their right to refuse and/or withdraw from the study at any time. In addition, study staff will emphasize that all study activities are entirely separate from routine ANC and postnatal care services received and that refusal or withdrawal from the study will have no impact on their ability to access any services provided at any public-sector health facility.

Inclusion of adolescent girls (16+ years old): Our study proposes to enroll pregnant adolescents 16 and 17 years old who will provide unassisted consent. The specific age range covers a critical period of risk of HIV acquisition. Further, *pregnant* adolescent girls are practicing condomless sex and are at elevated risk of HIV acquisition and mother to child transmission. Because of the high HIV incidence and existing policy supporting PrEP among adolescent girls, it would be unethical to not provide adolescent girls and young women with PrEP that might prevent them from acquiring HIV [18].

- All 16 and 17-year-old girls will provide unassisted consent if she chooses to participate.
- We will verify age on participant medical record and/or other official documents (eg, ID book)
- We will not have an upper age limit exclusion criterion for the study

Our definition of unassisted consent meets the following HREC conditions including:

- The study is no more than minimal risk; and

- The nature of the research is acceptable to the Committee, parents or legal guardians or the community at large.

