 - Our study was approved by the HREC and adolescent girl and young women PrEP is actively being rolled out in South Africa. In particular, we note that HREC has approved projects to use PrEP in adolescent girls ages 16-17 without parental consent in this area (see HREC REF: 567/2016).
- Justification for why adolescents are needed in the study:
 - Adolescent girls have high HIV incidence and pregnancy rates in South Africa. Girls 16-17 years old are at a critical period of risk of HIV acquisition. Because of the high HIV incidence and existing policy supporting PrEP among adolescent girls, it would be unethical to not provide adolescent girls and young women with PrEP that might prevent them from acquiring HIV
- Justification for why adolescents should consent unassisted.
 - Our formative research has demonstrated that adolescent girls do not attend antenatal care with their parent/guardian and may find it difficult to get parental consent. Further, our study will include sensitive surveys on sexual behaviours which the adolescent may not want to share with their parents or guardians.

Based on our work in this setting, we anticipate that young women ages 16-17 comprised <5% of all HIV-negative pregnant women at the Gugulethu MOU, and in turn we anticipate that this population will comprise <5% of our study cohort.

5. Study procedures

The study will be integrated into the MOUs. Women will be recruited directly from antenatal care. We will train existing counsellors, nurses and midwives in PrEP treatment (including risks and benefits) and the study. A trained recruiter will recruit directly from women at their first ANC visit, and if interested, women will go to the study trailer (Green Clinic) in Gugulethu for the consent and study enrolment procedures. Consented, enrolled women will be invited to return monthly for visits that correspond with their next ANC visit. All study staff will be trained, salaried staff working for UCT.

The purpose of the study visits will be to evaluate the study objectives. Below are the detailed steps for patient recruitment, enrolment, consent and study participation (Figure 5).

For enrolment/baseline visit

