As per the Department of Health. Guidelines for Good Practice in the Conduct of Clinical Trials with Human Participants in South Africa [21] we will collect parental or guardian consent to participate in the study as well as assent from the minor.

The risk is justified by the anticipated benefit to the subjects: the risks associated with PrEP-PP study procedures are minor and largely non-invasive (except for phlebotomy) and are justified by the anticipated benefit that PrEP would have on prevention of HIV acquisition in this vulnerable group. Thus, there is the potential for direct benefit associated with participation.

Informed consent

Informed consent for the study and questionnaire is modelled after that used in previous studies and will be delivered in participants' home language (isiXhosa or Afrikaans) by trained interviewers. This ICF details the purpose of the study, study procedures, and the risks and benefits to mothers that participants may encounter at the additional study measurement visit. This consent includes a separate specimen storage section. Participants who do not consent to specimen storage but who consent to the main study visit will still be able to complete the rest of the study.

Here, study staff will emphasize to participants that:

- Participation is entirely voluntary, and their choice regarding participation will in no way influence the quality of routine medical care for mothers or their infants
- Women may exit the study at any time for any reason without compromising the quality of health care received.

English versions of the informed consent documents are provided in the Appendix to this document. Translated isiXhosa and Afrikaans versions (as well as a certification of their translation and back-translation) will be submitted to the HREC before the start of the study.

Risks

The potential risks to participants in the study include:

- Risks associated with collection of self-reported behavioural and psychosocial information, related to psychosocial distress raised by questionnaire items involving social support, mental health, or disclosure of HIV status

- Risks due to loss of confidentiality due to study procedures—for instance, in the process of data collection
- Risk associated with asking participants to disclose their status, and potential for interpersonal violence by the partner resultant from the disclosure.

The potential risks to participants who take PrEP include:

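### The protocol gives incompatible consent rules for adolescents: unassisted consent at 16–17 in Section 4, parental or guardian consent in Section 7 and, for ages 16–19, in the background

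*Combined protocol and SAP*

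**What the plan says.** Consent by adolescents is described in three places in the current protocol text.

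- **Background, HIV and pregnancy in young women:** "Our study proposes to enroll pregnant adolescents 16-19 who have a parent or guardian who provides consent to their participation in the study".
- **Section 4 (Study population), Inclusion of adolescent girls:** "Our study proposes to enroll pregnant adolescents 16 and 17 years old who will provide unassisted consent". The rule is then stated without exception: "All 16 and 17-year-old girls will provide unassisted consent if she chooses to participate". One of the reasons given is that "adolescent girls do not attend antenatal care with their parent/guardian and may find it difficult to get parental consent"; another is that girls may not wish their parents to learn of their answers on sexual behaviour.
- **Section 7 (Ethical considerations), Ethics approach for including adolescent girls:** "we will collect parental or guardian consent to participate in the study as well as assent from the minor".

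Section 4 also states "We will not have an upper age limit exclusion criterion for the study", and its inclusion criteria set only a minimum age of 16, with no consent route. In Section 5, Step 5 of the enrolment visit has the study counselor read the form to the participant and check that she understands it before she signs. Nobody else signs. On numbers, Section 4 plans "N=220 pregnant women" and says of the 16- and 17-year-olds that "we anticipate that this population will comprise <5% of our study cohort".

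**The concern.** Whose consent makes a minor's enrolment valid should have one answer in a protocol. Here a girl of 17 who attends her first antenatal visit alone can be enrolled that day under Section 4, and cannot be enrolled under Section 7 until a parent or guardian has consented.

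Three things are at stake. The first is participant protection: this study offers a drug to pregnant minors, and under one of its own rules a minor's signature counts only as assent. The second is eligibility: the rule applied decides which adolescents may enter. The third is oversight: Internal monitoring in Section 7 commits the investigators to reviewing, on weekly calls, whether informed consent was completed, and for minors there is no single standard to review against.

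**Working it through.** The protocol states no figure for this point that could be reproduced. The check is a comparison of the texts, followed by the size of the affected group.

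**Step 1. Apply each rule to a woman attending alone.**

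| Age | Section 4 | Section 7 | Background |
|---|---|---|---|
| 16–17 | Own consent is enough | Parent or guardian must consent; she assents | Parent or guardian must consent |
| 18–19 | Not singled out | Refers to the minor, without giving an age | Parent or guardian must consent |
| 20 and over | Not singled out | Not affected | Not affected |

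The rows for 16–17 and for 18–19 both contain a conflict. Because there is no upper age limit, 18- and 19-year-olds are eligible by age under every version; only the condition attached to them changes.

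**Step 2. Can the rules be met together?** Collecting parental consent for every minor would satisfy Section 7, but it departs from the Section 4 rule that all 16- and 17-year-olds consent unassisted, and it sets aside the reasons given there. Relying on the girl's own consent satisfies Section 4 and breaches Section 7. No procedure meets both.

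**Step 3. Does other text settle it?**
- The inclusion criteria give age only.
- The enrolment steps fit Section 4, since only the participant signs, but they do not mention minors.
- Section 4 says the ethics committee approved the study and cites a different approved project that used unassisted consent at 16–17. It does not say that this study's approval covers that route.
- Ethical review in Section 7 describes approval by UCT-HREC and a second review by the UCLA IRB as still to come, and does not say which route either would accept.

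No passage gives one statement precedence over the others.

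**Step 4. Size of the affected group.** Inputs from Section 4: cohort 220, expected share aged 16–17 below 5%.

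0.05 × 220 = 11, so fewer than 11 women, that is at most 10.

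The share aged 18–19 is not given, so the extra group caught by the background wording cannot be counted.

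**Step 5. Effect on the cohort estimates.** Assume, for illustration, that all 10 girls were left out and that their PrEP initiation differed by 20 percentage points from that of the other women. The cohort proportion would shift by

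(10 / 220) × 20 = 0.9 points.

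The 95% half-width for a proportion of 50% with 220 women is

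1.96 × √(0.5 × 0.5 / 220) = 0.066, or 6.6 points.

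The shift is about one seventh of that half-width (0.9 / 6.6 = 0.14).

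**The case against.** The best defence is that the working parts of the protocol point one way. The eligibility list has no parental criterion, Section 4 gives an explicit and reasoned rule, the enrolment steps involve only the participant, and recruitment is by trained study staff at Gugulethu. On that view the sentences in the background and Section 7 are leftovers, and staff would not be misled. This may be so, but the protocol does not say it, and Section 7 is where an ethics body or monitor would look for the rule. If the sentences are leftovers, removing them is easy; it is still necessary. The consent forms and approvals were not available for this check. They might show which route was used, but they would not remove the conflict from the protocol body.

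The defence does succeed against several stronger readings that a reader might infer:

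- **That Section 7 is the governing section.** Nothing gives it precedence.
- **That data from minors enrolled on their own consent would have to be withdrawn.** No passage states that consequence.
- **That requiring parental consent would lose most of the minors.** Section 4 says only that consent may be difficult to get. Attending without a parent does not mean that a parent would refuse.
- **That those who remained would have parents aware of their PrEP use.** Under Section 5 a woman can join the study without taking PrEP, so consent to the study does not reveal use of the drug.
- **That the results would be biased.** At most 10 of 220 women aged 16–17 are affected, the outcome table in Section 6 has no adolescent-specific or disclosure outcome, and Section 6 describes the study as a pilot without power for differences at each step of the cascade.
- **That the two sections rest on contradictory risk categories.** Section 4 relies on a minimal-risk condition. Section 7 calls the risks minor and cites direct benefit, but names no category. The two are not shown to be incompatible.

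**Conclusion.** The conflict is real and must be resolved. The consent route for 16- and 17-year-olds differs between Section 4 on one side and Section 7 and the background on the other, and the background extends parental consent to 18- and 19-year-olds. As written, whichever route is used for a minor departs from some part of the protocol.

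The size is at most 10 of 220 women aged 16–17, plus an unknown number aged 18–19 if the background wording is followed. The count of 10 rests on the protocol's own expectation of under 5%. The importance lies in the validity of consent and the eligibility of minors. It does not lie in precision or bias: even under the 20-point assumption, a cohort proportion moves by less than one point.

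Which route is correct cannot be determined from these documents, and no view is taken on it.

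**What to change.** Check the existing approvals from UCT-HREC and the UCLA IRB and establish that both accepted the same consent route and age range. Then:

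1. State that one rule, with its age range, in Section 4, and delete or rewrite the conflicting sentences in the background and in Section 7. If the approved route involves a parent or guardian, it is the Section 4 text that changes.
2. Make Step 5 of the enrolment visit in Section 5 match the rule, so that it says who signs for a participant of each age.
3. Make the stated justification match the chosen route wherever it appears.
4. Use the same rule as the standard for the consent checks under Internal monitoring.

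If the two bodies approved different routes, that must be settled with them before the text is changed. Otherwise the cost is protocol wording and a look at approvals already held. The sample size and the planned analyses do not change.
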